3.0 PATIENT SELECTION

3.1 Inclusion Criteria

1. Histologically or cytologically confirmed high-grade metastatic sarcoma that has been stable on 6-12 cycles of one chemotherapeutic regimen (cytotoxic or biologic) although a change in chemotherapy is allowed if it is a result of toxicity/tolerability rather than progression. A patient must not have evidence of progression at any time while on chemotherapy in order to be eligible for this trial.
2. Measurable disease defined as lesions that can be accurately measured in at least one dimension (longest diameter to be recorded) as ≥ 10 mm with CT scan, PET CT, or MRI exam.
3. At least 18 years of age.
4. ECOG performance status ≤ 2 (Karnofsky $\geq 60\%$, see Appendix A)
5. Normal bone marrow and organ function as defined below:
 - a. Leukocytes $\geq 3,000/\text{mcl}$
 - b. Absolute neutrophil count $\geq 1,500/\text{mcl}$
 - c. Platelets $\geq 100,000/\text{mcl}$
 - d. Total bilirubin $\leq 1.5 \times \text{IULN}$ or $3 \times \text{IULN}$ with normal ALT and AST in patients with Gilbert's disease
 - e. $\text{AST(SGOT)/ALT(SGPT)} \leq 3.0 \times \text{IULN}$

- f. Creatinine less than the institutional upper limit of normal
OR
Creatinine clearance ≥ 50 mL/min/1.73 m²
 - g. INR < 1.5 or patient off Coumadin at the time of ablation
6. No more than 10 treatable lesions as evaluated by an experienced interventional oncologic radiologist for eligibility and lesion accessibility as the ablation of more than 10 lesions becomes technically infeasible. These lesions must be treated in a two- to three-week time period from initial interventional radiology evaluation. Lung and liver lesions can range from 1 cm to 7 cm for a single lesion and no greater than 5 cm for multiple lesions. There are no size criteria for the osseous lesions.
 7. The lesions will be amenable to a safe, ultrasound/computed tomographic/fluoroscopic guided percutaneous approach. The targeted metastases must be sufficiently separateable from the central nervous system, major peripheral motor nerves, bowel, and bladder. All lesions must be amenable to treatment.
 8. If patients have received radiation therapy, there must be a one-month washout period.
 9. Women of childbearing potential and men must agree to use adequate contraception (hormonal or barrier method of birth control, abstinence) prior to study entry and for the duration of ablation. Should a woman become pregnant or suspect she is pregnant while participating in this study, she must inform her treating physician immediately.
 10. Patient (or legally authorized representative if applicable) must be able to understand and willing to sign an IRB approved written informed consent document.

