5.4 Criteria for Ablation

Ablation will be postponed for ANC<1500 or platelets <100,000. Ablation will also be postponed if the creatinine or bilirubin are elevated above baseline until those lab values normalize.

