5.5 Evaluation for Severity of Pain and Quality of Life

Patients will be evaluated for severity of pain using the BPI-Short Form (Appendix B) with the assistance of a study coordinator at the following time points:

- Prior to ablation
- 1 day post-ablation
- 1 month post-ablation – from first procedure if more than 1 is done
- Time of disease progression

The patients are asked to answer the questions with respect to the lesion(s) treated. They are not given a copy of the BPI-Short Form and no prior responses are available to review on subsequent visits to minimize bias. Analgesic use following the tumor ablation will be recorded as well.

Patients will be evaluated on quality of life based on the FACT-G7 survey (Appendix C) with the assistance of the study coordinator at the following time points:

- Prior to ablation
- 1 day post-ablation
- 1 month post-ablation – from first procedure if more than 1 done
- Time of disease progression

They are not given a copy of the FACT-G7 form and no prior responses are available to review on subsequent visits to minimize bias.

These surveys may be administered over the phone.

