5.7 General Concomitant Medication and Supportive Care Guidelines

No restrictions to medications exist with regards to the ablation procedures. However, clopidogrel (anti-platelet medication) should be discontinued for 5-7 days pre-procedure, unless the risk of discontinuation outweighs the risk of bleeding. Blood thinners such as warfarin should be discontinued for 5-7 days prior to the procedure as well.

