5.8 Women of Childbearing Potential

Women of childbearing potential (women with regular menses, women with amenorrhea, women with irregular cycles, women using a contraceptive method that precludes

withdrawal bleeding, and women who have had a tubal ligation) are required to have a negative pregnancy test (serum or urine) within 1 day prior to the ablation procedure.

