7.0 STUDY CALENDAR

Baseline evaluations are to be conducted within 3 weeks prior to start of protocol therapy. Scans and x-rays must be done no more than 3 weeks prior to the start of ablation.

	Baseline	Ablation	1 day after ablation	1 month after ablation	Follow-up ^d	Progression
Physical exam, incl. medical history, weight, VS, PS	X					
CBC	X					
CMP	X					
PT/PTT and INR	X					
Pregnancy test ^a	X					
IR evaluation ^b	X					
CT or PET scan					X ^d	
FACT-G7	X		X	X		X
BPI short form	X		X	X		X
Adverse events		X ^c				
Survival follow-up						X ^e

a: Women of childbearing potential only

b: Patients must have 10 or fewer treatable lesions when enrolled in the study and will be seen in consultation by an experienced interventional oncologic radiologist with evaluation of available PET, CT, MR, and US images for eligibility and lesion accessibility

c: Tracked for 30 days following ablation

d: The patients will be imaged as per routine care at the following time points: 6 weeks post first-procedure, every 9 weeks for the first year, every 12 weeks for the second year, and every 6 months for 5 years or until death or radiographic progression, whichever comes first.

e. After progression, patients will be followed every 3 months for survival only.

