9.0 MEASUREMENT OF EFFECT

9.1 Antitumor Effect – Solid Tumors

There will be another PET/CT at 42 +/- 3 days following the last procedure (approximately 6 weeks post-procedure) and one every 9 weeks thereafter until progression of disease. All imaging is standard of care.

For the purposes of this study, patients should be re-evaluated for response every 9 weeks. In addition to a baseline scan, confirmatory scans should also be obtained 4 weeks (not less than 4) weeks following initial documentation of objective response.

Response and progression will be evaluated in this study using the new international criteria proposed by the revised Response Evaluation Criteria in Solid Tumors (RECIST) guideline (version 1.1) [Eur J Ca 45:228-247, 2009]. Changes in the largest diameter (unidimensional measurement) of the tumor lesions and the shortest diameter in the case of malignant lymph nodes are used in the RECIST criteria.

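### Item 5g drops the INR limit for a warfarin user who has stopped the drug, and no written rule checks the INR before ablation

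*Combined protocol and SAP*

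**What the plan says.** Five places in the combined protocol and SAP bear on coagulation before ablation.

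- **Section 3.1, item 5g** sets the entry rule: "INR < 1.5 or patient off Coumadin at the time of ablation".
- **Section 5.7** gives the drug stop: "Blood thinners such as warfarin should be discontinued for 5-7 days prior to the procedure as well". It asks for no INR after the stop and says nothing about when warfarin may be resumed.
- **Section 7.0 (Study Calendar)** has one mark for PT/PTT and INR, in the baseline column. On timing it says: "Baseline evaluations are to be conducted within 3 weeks prior to start of protocol therapy". The ablation column carries no INR.
- **Section 5.4** holds the procedure for blood counts ("Ablation will be postponed for ANC<1500 or platelets <100,000") and for chemistry ("Ablation will also be postponed if the creatinine or bilirubin are elevated above baseline until those lab values normalize"). INR is not named.
- **Sections 5.5 and 9.1** allow for more than one session, although section 5.9 describes ablation as a single event. Section 5.5 times the one-month survey "from first procedure if more than 1 is done", and section 9.1 says: "There will be another PET/CT at 42 +/- 3 days following the last procedure".

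**The concern.** The protocol sets an INR below 1.5 as its coagulation limit and then, through the word joining the two limbs of 5g, lifts that limit for any patient who has stopped warfarin. Those are the patients in whom a raised INR is most to be expected. For them the protocol relies on a drug-free interval and never asks whether the interval had its intended effect.

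What is at stake is procedural bleeding. Sections 5.1 to 5.3 describe probes placed through the skin into lung, liver, bone, soft tissue and spinal lesions. Section 5.1 also allows temperature sensors in the epidural space when neural structures need protection. The gap is one of verification: a stated limit exists, and no written step confirms that it is met before the procedure.

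**Working it through.** No sample size, error rate or event count enters this point, and the plan gives no figure to reproduce. The check sets the rules side by side and follows one patient through them.

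**One patient through the rules.** Take a warfarin user whose screening INR is 1.5 or more.

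1. *Entry (5g).* The first limb fails. The second is met if warfarin has been stopped by the time of ablation, and it carries no INR value. The patient qualifies at any INR.
2. *Drug stop (5.7).* Warfarin should be stopped 5-7 days before. This is worded as advice and prescribes an interval, not a laboratory result.
3. *Calendar (7.0).* The only scheduled INR may be drawn up to 3 weeks (21 days) before therapy. Since 21 days is longer than 5-7 days, the value may date from before the stop. It may also fall after the stop, but nothing requires this.
4. *Hold (5.4).* Even if a baseline INR is drawn after the stop and is still 1.5 or more, entry by the second limb stands and no hold applies.
5. *Later sessions (5.5, 9.1).* No further INR is scheduled. This matters for these patients mainly if warfarin is restarted between sessions, which the protocol does not address.

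Result: a patient with an INR of 1.5 or more on the day of ablation can satisfy every written rule.

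**How other tests are handled.**

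| Test | Entry rule in 3.1 | Calendar mark | Hold in 5.4 | Dated repeat before ablation |
|---|---|---|---|---|
| ANC, platelets | Limit | Baseline | Yes | None |
| Creatinine, bilirubin | Limit | Baseline | Yes, relative to baseline | None dated; a retest is implied |
| Leukocytes, AST/ALT | Limit | Baseline (in CBC, CMP) | No | None |
| INR | Limit, or off warfarin | Baseline | No | None |

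The pregnancy test is the only one with a dated slot: section 5.8 requires a "negative pregnancy test (serum or urine) within 1 day prior to the ablation procedure".

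INR is thus not the only test without a hold or a scheduled repeat. It differs from the other laboratory tests in the table in one respect: its entry limit can be bypassed at any value by stopping a drug, with no repeat test to close the loop.

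**The case against.** The strongest defence is that the protocol does have a control and that this point merely prefers another. Being off warfarin is tied to the procedure itself, section 5.7 gives it a duration, and relying on a washout rather than a laboratory check is a clinical choice. In addition, item 7 requires that lesions be safely approachable, an experienced interventional radiologist evaluates every patient, and section 5.9 stops treatment if the protocol's constraints would harm the patient. In practice a radiologist may well check the INR.

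Much of this stands. These safeguards lower the risk, and the documents do not say how often an INR remains at 1.5 or more after such a stop. But none of them checks the INR, and the protocol itself chose a numerical limit. For platelets it did not rely on judgment alone: it wrote both an entry limit and a hold.

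Three stronger readings are tempting and are not supported:

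- *That INR alone was overlooked.* Section 5.4 schedules no repeat CBC or CMP and does not cover leukocytes or AST/ALT, so the contrast with other tests is limited.
- *That the protocol means to admit patients never on warfarin who have a raised INR.* The literal wording permits it, but it is unlikely to be the intent. It is a drafting side-effect that the rewording below removes.
- *That patients will be ablated while anticoagulated, or that excess bleeding should be expected.* The documents give no rate from which to infer this.

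**Conclusion.** The point holds as a minor safety correction. On the written rules, a warfarin user can reach ablation with an INR of 1.5 or more and no deviation from protocol. This rests on the plain reading of the two limbs of 5g as alternatives and on the absence of any INR requirement in sections 5.4, 5.7 and the ablation column of the calendar.

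The size cannot be derived. The number affected is at most the number of warfarin users enrolled with a raised screening INR, which the documents do not give. That it is small is an assumption. A reader might also infer that the efficacy result is compromised. It is not: the 3-month progression-free rate, its null and alternative values, and the enrolment of 36 do not depend on this rule.

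**What to change.** Three linked wording changes:

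1. **Item 5g:** *INR < 1.5; a patient on warfarin with a higher screening INR may enrol only if warfarin is stopped as in 5.7 and a repeat INR after the stop and before ablation is < 1.5.*
2. **Section 5.4:** *In a warfarin user, ablation is postponed while the most recent INR is 1.5 or more.* The hold need not extend to other patients, because under the reworded 5g a non-user with an INR of 1.5 or more is already ineligible.
3. **Section 7.0:** add an INR for warfarin users after the stop and before ablation, repeated before a later session if warfarin was restarted. The slot within 1 day before ablation that section 5.8 uses for the pregnancy test could serve.

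Whether 1.5 remains the right limit, and the exact timing, are for the sponsor and the treating radiologists.

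The cost is amendment wording, one routine blood test for warfarin users, and an occasional short deferral. A deferral must fit the two to three weeks that item 6 of section 3.1 allows from the radiology evaluation. If the stop begins at that evaluation, the time left after it runs from 14 - 7 = 7 days to 21 - 5 = 16 days. A deferral also lengthens the time off warfarin, which the treating physician must weigh against the bleeding risk.

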3.2 Exclusion Criteria

1. History of other malignancy ≤ 5 years previous with the exception of basal cell or squamous cell carcinoma of the skin which were treated with local resection only, carcinoma *in situ* of the cervix, or localized prostate cancer.
2. Receiving any other investigational agents simultaneously or within 3 weeks following ablation procedure.
3. Known brain metastases. Patients with known brain metastases must be excluded from this clinical trial because of their poor prognosis and because they often develop progressive neurologic dysfunction that would confound the evaluation of neurologic and other adverse events.
4. Intercurrent illness including, but not limited to, ongoing or active infection, symptomatic congestive heart failure, unstable angina pectoris, cardiac arrhythmia, or psychiatric illness/social situations that would limit compliance with study requirements.

5. Pregnant and/or breastfeeding.
6. Patients whose treatment plans include continuing chemotherapy after ablation as per the treating physician, as ablation therapy is meant to serve as maintenance therapy in lieu of chemotherapy.

3.3 Inclusion of Women and Minorities

Both men and women and members of all races and ethnic groups are eligible for this trial.

4.0 REGISTRATION PROCEDURES

Patients must not start any protocol intervention prior to registration through the Siteman Cancer Center.

The following steps must be taken before registering patients to this study:

1. Confirmation of patient eligibility
2. Registration of patient in the Siteman Cancer Center OnCore database
3. Assignment of unique patient number (UPN)

4.1 Confirmation of Patient Eligibility

Confirm patient eligibility collecting the information listed below:

1. Registering MD's name
2. Patient's race, sex, and DOB
3. Three letters (or two letters and a dash) for the patient's initials
4. Copy of signed consent form
5. Completed eligibility checklist, signed and dated by a member of the study team
6. Copy of appropriate source documentation confirming patient eligibility

4.2 Patient Registration in the Siteman Cancer Center OnCore Database

All patients must be registered through the Siteman Cancer Center OnCore database.

4.3 Assignment of UPN

Each patient will be identified with a unique patient number (UPN) for this study. All data will be recorded with this identification number on the appropriate CRFs.

5.0 TREATMENT PLAN

Eligible patients will have their lesions ablated using any one or more of the procedures described below. The choice of the procedure will be based on the expertise of the interventional oncologic radiologist and the site of metastasis. These techniques are thought to be equivalent.

Pre-and post procedure, patients must fill out a QOL survey and Brief Pain Inventory (BPI)-Short form, which is a validated visual analog scale for assessment of patient pain asking the patient to rate his/her worst pain in 24 hours. These surveys can be done over the phone.

5.1 Cryoablation

Cryoablation is performed under ultrasound, CT and occasional fluoroscopic guidance with CT fluoroscopy available for intermittent use in cyroprobe placement and CT monitoring of ablation. Procedures will be performed on an outpatient basis, but patients can be admitted for observation post-procedure as deemed appropriate by the treating interventional radiologist. Patients are generally under moderate conscious sedation with midazolam and fentanyl with continuous nurse monitoring of pulse oximetry, blood pressure, cardiac rhythm and rate, and respirations. General endotracheal anesthesia is allowed in cases felt clinically appropriate as deemed by the interventional radiologist. One percent lidocaine alone or a 1:1 mixture of 1% lidocaine and 0.25% bupivacaine or 0.5% ropivacaine is used for local and periosteal anesthesia.

Cryoprobes from Endocare Inc. (Irvine CA) or Galil Medical (Arden Hills MN) are either introduced into the lesion co-axially through a bone biopsy needle or directly into the lesions that are amenable to such, i.e., soft tissue, lung, liver, and large lytic lesions with extensive bone destruction. For blastic lesions, a hand drill may be needed for bone access. For larger lesions, additional cryoprobes are placed in parallel arrangement approximately 1.0 cm apart. The Cryocare Surgical System allows the operation of up to twenty-five cryoprobes at a time through 5 controllable channels. The Endocare system allows for the independent operation of up to 16 cryoprobes at a time. Cryoprobe positioning and adequate coverage of bone-tumor interface is confirmed with CT imaging. When necessary thermal protection and temperature monitoring of neural structures is performed and includes placement of thermocouples in the neural foramen and epidural space at the level of the lesion and injection of warm saline or carbon dioxide for thermal insulation. Bowel protection with balloon interposition or with carbon dioxide dissection will be used if necessary.

A single freeze-thaw-freeze cycle is performed for each lesion at 10 minutes, 8 minutes, and 10 minutes, respectively. The freezing portions of the cycle may vary depending on size of the ice-ball and adequacy of coverage and proximity to adjacent critical structures. Non-enhanced computed tomography is performed every 3 to 5 minutes with soft tissue windows (400 HU window, 40 HU level) throughout the freezing cycle to monitor growth of the ice ball. After completion of the final freeze cycle of the cryoablation procedure, the cryoprobes are actively heated with helium until temperature is above 20 degrees Celsius and then the probe is withdrawn.

5.2 Radiofrequency Ablation

Radiofrequency ablation will be predominantly used on metastatic spine lesions and will include use of the Dfine STAR ablation probe. This probe will be placed coaxially through an introducer needle into the spinal metastatic lesion. Time and area of kill is based on temperatures measured at both proximal and distal thermocouples on the probe. The ablation will usually be followed by placement of high viscosity cement for treatment of a fracture or lesions at risk.

5.3 Microwave Ablation

Microwave ablation will be predominantly used on metastatic soft tissue lesions and will include use of Covidien's Evident™ MWA System. Microwave ablation is performed under ultrasound, CT, and occasional fluoroscopic guidance with CT fluoroscopy available for intermittent use in probe placement and CT monitoring of ablation. Procedures will be performed on an outpatient basis, but patients can be admitted for observation post-procedure as deemed appropriate by the treating interventional radiologist. Patients are generally under moderate conscious sedation with midazolam and fentanyl with continuous nurse monitoring of pulse oximetry, blood pressure, cardiac rhythm and rate, and respirations. General endotracheal anesthesia is allowed in cases felt clinically appropriate as deemed by the interventional radiologist. One percent lidocaine alone or a 1:1 mixture of 1% lidocaine and 0.25% bupivacaine or 0.5% ropivacaine is used for local and periosteal anesthesia.

Microwave antennae from Covidien (Mansfield, MA) are either introduced into the lesion co-axially through a bone biopsy needle or directly into the lesions that are amenable to such, i.e., soft tissue, lung, liver, and large lytic lesions with extensive bone destruction. For blastic lesions, a hand drill may be needed for bone access. For larger lesions, additional antennae are placed in parallel arrangement approximately 1.0 cm apart. Antenna positioning and adequate coverage of the tumor is confirmed with CT imaging. When necessary, thermal protection and bowel protection with balloon interposition or with carbon dioxide dissection or hydrodissection will be used.

Ablations will be performed according to the manufacturer's recommendations in the package insert. After completion of ablation, tract ablation is performed as the probe is withdrawn.

5.4 Criteria for Ablation

Ablation will be postponed for ANC<1500 or platelets <100,000. Ablation will also be postponed if the creatinine or bilirubin are elevated above baseline until those lab values normalize.

5.5 Evaluation for Severity of Pain and Quality of Life

Patients will be evaluated for severity of pain using the BPI-Short Form (Appendix B) with the assistance of a study coordinator at the following time points:

- Prior to ablation
- 1 day post-ablation
- 1 month post-ablation – from first procedure if more than 1 is done
- Time of disease progression

The patients are asked to answer the questions with respect to the lesion(s) treated. They are not given a copy of the BPI-Short Form and no prior responses are available to review on subsequent visits to minimize bias. Analgesic use following the tumor ablation will be recorded as well.

Patients will be evaluated on quality of life based on the FACT-G7 survey (Appendix C) with the assistance of the study coordinator at the following time points:

- Prior to ablation
- 1 day post-ablation
- 1 month post-ablation – from first procedure if more than 1 done
- Time of disease progression

They are not given a copy of the FACT-G7 form and no prior responses are available to review on subsequent visits to minimize bias.

These surveys may be administered over the phone.

